10.18 Multiple Sclerosis Spasticity Scale (MSSS-88)

The MSSS-88 will be completed at Day 1 Visit (baseline), Visit 5 (Week 8) and Visit 6 (Week 12/early withdrawal). Eight sub-scales representing 8 domains will be derived by summing each of the constitutive items provided that at least 50% of the items are answered, items with a missing score will be replaced by the mean score of the items completed within the same domain for subscale scores. The total score will only be calculated if, after applying the imputation, all 8 sub-scales have a score, otherwise will be set to missing.

The questions will be grouped as follows:

- 3 spasticity specific symptoms
 - Muscle Stiffness: sum of questions 1 to 12
 - Pain and Discomfort: sum of questions 13 to 21
 - Muscle Spasms: sum of questions 22 to 35
- 3 areas of physical functioning
 - Activity of Daily living (ADL): sum of questions 36 to 46
 - Ability to Walk: sum of questions 47 to 56
 - Body Movement: sum of questions 57 to 67
- 2 area of psychosocial impact
 - Emotional health: sum of questions 68 to 80
 - Social Functioning: sum of questions 81 to 88
- Total score
 - Sum of the 88 questions

Table 10.18-1	Multiple Sclerosis S	pasticity Scale	- Missing	g Data Handling
---------------	-----------------------------	-----------------	-----------	-----------------

Subscale and total score	Number of questions included in subscale and total score	Minimum number of questions required for score derivation (at least 50%)
Muscle Stiffness	12	6
Pain and Discomfort	9	5
Muscle Spasms	14	7
Activity of Daily living (ADL)	11	6
Ability to Walk	10	5
Body Movement	11	6
Emotional health	13	7
Social Functioning	8	4
Total score	88	NA will only be calculated if minimum number of questions met for each subscale

10.19 Numerical Rating Scale (NRS) for Spasm Severity

The NRS spasm severity score is collected daily via eDiary and is on a scale from 0 to 10. The average NRS spasm severity score will be derived for each patient for the following periods: the baseline period, the three 4-week periods in the randomized period (Week 1 to 4, Week 5 to 8 and Week 9 to 12), the follow-up baseline period and the follow-up period (definitions for the periods and baseline are described in Section 10.2.2 and Section 10.4.1).

The average NRS spasm severity score for each period is defined as follows:

Sum of the NRS spasm severity score for the period Number of days in which the daily diary was completed during the period

The average NRS spasm severity score will be set to missing under the following conditions:

- if less (<) than 15 days with non-missing data and more than or equal to (≥) 10 consecutive days with missing data for the three 4-week periods in the randomized period.
- if less (<) than 7 days with non-missing data and more than or equal to (≥) 5 consecutive days with missing data for the follow-up period.

The change from baseline will then be calculated (as described in Section 10.5) for the three 4-week periods in the randomized period and the follow-up period.

10.20 Numerical Rating Scale (NRS) for Spasticity

The NRS spasticity score is collected daily via eDiary and is on a scale from 0 to 10. The average NRS spasticity score will be derived for each patient for the following periods: the baseline period, the twelve 1-week periods in the randomized period, the follow-up baseline period and the two 1-week follow-up periods (definitions for the periods and baseline are described in Section 10.2.2 and Section 10.4.1).

The average NRS spasticity score for each period is defined as follows:

Sum of the NRS spasticity score for the period Number of days in which the daily diary was completed during the period

The non-baseline average NRS spasticity score will be set to missing under the following conditions:

• if less (<) than 3 days with non-missing data and more than or equal to (≥) 3 consecutive days with missing data.

The change from baseline will then be calculated (as described in Section 10.5) for the twelve 1-week periods in the randomized period and the two 1-week periods in the follow-up period.

10.21 Timed 25-Foot Walk

The Timed 25-Foot Walk (T25FW) is the time needed for a patient to walk 25-feet. The test consists of two trials separated by a 5-minute rest period. The maximum duration of each trial is set to 3 minutes (180 seconds).

The average timed 25-foot walk (expressed in seconds) will be derived for each patient as the average of the two trials recorded at Day 1 Visit (baseline) and Visit 6 (Week12/early withdrawal).

If a patient only performs 1 of the 2 trials at a given timepoint, the unperformed trial will be imputed as 180 seconds.

If a patient is not using the same assistive device or introduces a new assistive device between pre- and post-randomisation assessment, the post-randomisation average T25FW will be set to missing.

The change from baseline will then be calculated (as respectively described in Section 10.5 and in Section 10.6).

10.22 36-Item Short Form Health Survey

The SF-36 is a 36-item instrument. Items are divided into eight concepts plus one health comparison question.

The programming team will use the Enterprise Version of PRO CoRE software by Optum to score the SF-36.

The raw scale scores are computed by summing item responses within each concept after recoding the individual item if needed.

The eight concepts to be scored are:

- Physical Functioning (PF) (items 3a-3j): The ten items are coded as 1-3. There is no recoding needed.
 The lowest possible raw score is 10, the highest is 30 and the range is 20. High score indicates
 - The lowest possible raw score is 10, the highest is 30 and the range is 20. High score indicates better PF.
- Role-Physical (RP) (items 4a-4d): The items are coded as 1-5. There is no recoding needed. The lowest possible raw score is 4, the highest is 20 and the range is 16. High score indicates better Role- Physical function.
- Role-Emotional (RE) (items 5a-5c): The items are coded as 1-5. There is no recoding needed. The lowest possible raw score is 3, the highest is 15 and the range is 12. High score indicates better Role-Emotional function.
- Social Functioning (SF) (items 6, 10): The items are coded as 1-5. Item 6 is recoded as 5-1. Item 10 does not require recoding value.
 The lowest possible raw score is 2, the highest is 10 and the range is 8. High score indicates better social functioning.
- Bodily Pain (BP) (items 7 & 8): This concept requires special coding. Item 7 is coded as 1-6 and is recoded as 6.0, 5.4, 4.2, 3.1, 2.2, 1.0. Item 8 is coded as 1-5 and is recoded as 6-1 if both item 7 and item 8 are answered. If item 7 is not answered, item 8 is recoded as 6.0, 4.75, 3.5, 2.25, 1.0.

The lowest possible raw score is 2, the highest is 12 and the range is 10. High score indicates lack of bodily pain.

- Mental Health (MH) (items 9b, 9c, 9d, 9f & 9h). The items are coded as 1-5. Items 9b, 9c and 9f do not require recoding. Items 9d and 9h are recoded as 5-1.
 The lowest possible raw score is 5, the highest is 25 and the range is 20. High score indicates better mental health.
- Vitality (VT) (items 9a, 9e, 9g, 9i): The items are coded as 1-5. Items 9a and 9e are recoded as 5-1. Items 9g and 9i do not require recoding. The lowest possible raw score is 4, the highest is 20, the range is 16. High score indicates more vitality.
- General Health (GH) (items 1, 11a-11d): The items are coded as 1-5. Items 11a and 11c do not require recoding. Items 11b and 11d are recoded as 5-1.
 Item 1 is recoded as 5.0, 4.4, 3.4, 2.0, 1.0.
 The lowest possible raw score is 5, the highest is 25 and the range is 20. High score indicates better general health perceptions.
- Reported Health Transition (HT) (item 2). Item 2 is coded as 1-5 and is recoded 5-1.
- In addition to the concepts above, the scoring software also provides results for two aggregate scores:
 - Physical Component Summary (PCS)

• Mental Component Summary (MCS).

Any out-of-range value will be considered missing.

Missing or blank values will be estimated using the Full missing score estimation (as defined in scoring PRO CoRE software manual).

The formula for the transformed scale = [(actual raw score – lowest possible raw score)/Possible raw score range] x 100.The raw scores will be transformed to a 0 to 100 scale.

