#### SPONSOR: GW PHARMA LIMITED

# 9.2.15.3 Timed 25-Foot Walk

The T25FW is a quantitative measure of lower extremity function and should be performed by a trained assessor. The same assessor should administer the T25FW test throughout the trial where possible. If ambulatory, the patient will be instructed to begin at one end of a clearly marked 25-foot course. They will be instructed to walk the 25 feet as quickly as possible, but safely, and to not slow down until after they have passed the finish line. The task will be immediately administered a second time following the first trial by having the patient walk back the same distance.

Patients will be permitted to use their customary, nonmotorized assistive device (AD) (cane, walking sticks, walker, and rollator) during the T25FW test. The same AD must be used at each assessment and its use documented in the patient record.

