10.5 Change from Baseline

Change from baseline (CFB) is defined as:

post-baseline – baseline

CFB will be calculated only for patients with both a baseline and post-baseline value.

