12.5.4.4 Timed 25-foot Walk

A decrease in average time to complete the two trials will show an improvement.

The change from baseline to Week 12 in average timed 25-foot walk (as described in Section 10.5) will be analyzed during the 12-week randomized period using ANCOVA performed with the SAS® MIXED procedure.

This model will include all patients belonging to the FAS with a baseline average T25FW (as defined in Section 10.4.1) and at least one post-baseline average T25FW value (as described in Section 10.21). In case of premature study discontinuation before Week 12, averageT25FW values will be imputed using a last observation carried forwards (LOCF) methodology.

The preferred model will include the fixed categorical effects of treatment arm, randomization strata of prior cannabis use and randomization strata of region as well as, the baseline average T25FW as covariate.

The treatment arm will have 2 levels: nabiximols and placebo.

The randomization strata of prior cannabis use will have 2 levels: Yes and No.

The randomization strata of region will have 2 levels: USA and non-USA.

Stratification classification will be obtained from the 'Randomization eCRF' page as this will show the true classification in case of mis-stratification.

This model will provide the LS mean estimates for each treatment arm, along with the standard errors and 95% confidence intervals (CIs) as well as, the least squares mean estimates of the mean treatment difference in change from baseline in average T25FW with the standard error of the difference and 95% CI. T-statistics corresponding to the Type III sum of squares for difference in LS means will be used to obtained nominal p-value for treatment arm comparison at Week 12.

In case of non-convergence of the preferred model or memory space issue a back-up model will be used removing some of the randomization strata as mentioned in Section 12.0.

Additionally, a plot of LS mean change from baseline and corresponding 95% CI at Week 12 per treatment arm.

Descriptive statistics for the average T25FW values and change from baseline by treatment arm will be provided. A by-patient listing presenting observed and derived variables will be presented.

A patient listing presenting observed and derived variables will be presented.

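### SAP 10.21 scores an unperformed Timed 25-Foot Walk trial as 180 s whenever the other trial was done, at baseline as well as Visit 6, so the derived average is off by (180 − t)/2

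*SAP*

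**What the plan says.** SAP 10.21 averages two timed trials at the Day 1 visit and again at Visit 6, and caps each trial at 3 minutes. For a single missing trial it says: "If a patient only performs 1 of the 2 trials at a given timepoint, the unperformed trial will be imputed as 180 seconds". Neither SAP 12.5.4.4 nor Protocol 9.2.15.3 narrows this by reason or by visit. The rule does not apply when neither walk is performed. If the assistive device changes or a new one is introduced, SAP 10.21 takes another course: "the post-randomisation average T25FW will be set to missing".

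On change scores, SAP 10.5 says: "CFB will be calculated only for patients with both a baseline and post-baseline value". On direction, SAP 12.5.4.4 says: "A decrease in average time to complete the two trials will show an improvement". That section plans an ANCOVA with the baseline average as covariate, and a by-patient listing of observed and derived values. Table 7-1 of the SAP addendum reduces T25FW to listings and keeps 12.5.4.4 as the reference for them.

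The two documents also describe the repeat walk differently. SAP 10.21: "The test consists of two trials separated by a 5-minute rest period". Protocol 9.2.15.3: "The task will be immediately administered a second time following the first trial". SAP 6.2 reports no change from the protocol.

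**The concern.** The trigger is that a walk was not performed, not that the patient was unable to walk. A repeat missed for lack of time, a timing failure or a refusal gets the same 180 s as a patient who could not manage it. The completed walk, which is a direct measurement, then counts for only half of a score whose other half is the maximum time.

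A worst-value convention is normally defended as conservative. At baseline it is not: it makes the patient look slow before treatment and improved afterwards. The rule also ranks patients oddly. Someone who walked once at normal speed receives a very poor score, while someone who performed neither walk receives no 180 s from this rule, and someone who took up a new assistive device is set to missing.

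It also differs from how the SAP handles gaps elsewhere. Missing MSSS-88 items take the mean of the completed items in the domain (10.18), and diary averages divide by the days completed (10.17, 10.19, 10.20).

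At stake is whether the derived T25FW average and change describe walking speed for any patient with one missing trial.

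**Working it through.** **Inputs.** The imputed value is 180 s (SAP 10.21), which equals the cap of 3 × 60 s. The visit score is the mean of two trials (10.21). Change is post-baseline minus baseline (10.5), and a decrease is improvement (12.5.4.4). The documents give no walk times, so t is an assumption and is shown over a range. There is no computed T25FW figure in the plan to reproduce.

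**Shift for one missing trial.** The derived average is (t + 180)/2. Its distance from the observed walk is (t + 180)/2 − t = (180 − t)/2.

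| Completed walk t (s) | Derived average (s) | Shift (s) |
|---|---|---|
| 6 | 93 | 87 |
| 8 | 94 | 86 |
| 15 | 97.5 | 82.5 |
| 20 | 100 | 80 |
| 30 | 105 | 75 |
| 60 | 120 | 60 |
| 120 | 150 | 30 |
| 180 | 180 | 0 |

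**Effect on change.** Take a patient who walks in 20 s at both visits, so the true change is 0.
- Repeat missed at Visit 6 only: 100 − 20 = +80 s, apparent worsening.
- Repeat missed at baseline only: 20 − 100 = −80 s, apparent improvement.
- Repeat missed at both visits: 100 − 100 = 0.

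**Effect under SAP V1.0, had the ANCOVA been run.** One miss at Visit 6 moves that arm's raw mean change by (180 − t)/(2n):
- t = 20 s and n = 223, the planned arm size: 80/223 = 0.36 s. Five such patients give 400/223 = 1.79 s.
- t = 8 s and an assumed 150 ambulatory patients per arm: 86/150 = 0.57 s. With an assumed 75: 86/75 = 1.15 s.

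The 223 is generous, because non-ambulatory patients do not do the test and the trial stopped early. For a miss at baseline the false value is also the ANCOVA covariate, so the adjusted effect is not simply the shift divided by n.

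**Effect under the addendum.** No T25FW arm mean, variance or model is produced. What remains is the derived average and change in the listing for each affected patient, wrong by the amounts in the table.

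**Comparing rules.** Suppose a patient completes one 30 s walk at each visit and physically cannot repeat it either time, with no real change.
- Current rule: 105 − 105 = 0.
- 180 s for inability at Visit 6 only: 105 − 30 = +75 s, a false worsening.
- Completed walk used at both visits: 30 − 30 = 0.

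The last rule also gives 0 for the 20 s patient above, whichever visit lacks the repeat.

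**The case against.** The best defence is that 180 s is a deliberate worst score. The protocol has the patient walk straight back and exempts non-ambulatory patients from the test, so inability to return is a plausible reason for a missing repeat. The SAP reference list includes a functional-composite scoring manual that is not available here, and the convention or the rest period may come from it. No document says how often a single trial is missing; the count may be zero.

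Much of this stands. Frequency is unknown, and penalising inability at Visit 6 is a coherent choice. But the rule is not written as an inability rule, and the defence does not cover baseline, where the imputed value produces apparent benefit.

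It is also fair that T25FW is exploratory and outside the testing hierarchy, and that the listing shows observed as well as derived values. If trial-level times are listed, a careful reader can spot the artefact.

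A reader might infer three stronger things that the documents do not support:
- **That a reported treatment comparison is compromised.** The addendum removes all T25FW descriptive and inferential statistics.
- **That the error is always about 80 s.** It depends on t and falls to zero as t approaches 180 s.
- **That the rule favours nabiximols.** The sign depends on which visit lacks the walk, not on the arm.

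**Conclusion.** The point holds as a derivation error of low severity. The rule is explicit, it applies whatever the reason and at either visit, and the resulting value does not measure walking speed. The 75 to 87 s size rests on the assumed completed-walk times of 6 to 30 s; the formula itself needs no assumption. The arm-mean figures also rest on assumed walk times and arm sizes, and describe only what SAP V1.0 would have produced. Under the addendum the consequence is confined to listed averages and changes for an unknown, possibly zero, number of patients. The rest-period discrepancy is a separate wording conflict and does not enter the calculation.

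**What to change.** In SAP 10.21, delete the 180 s imputation for unperformed trials. State instead that when only one of the two trials is performed, its time is the visit value, with the same rule at baseline and at Visit 6.

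If the sponsor wishes to keep a 180 s score for a walk attempted but not completed within the 3-minute maximum, it should apply identically at both visits. Restricting it to post-baseline creates the false worsening shown above. Any rule that depends on why a trial was missed would need a reason recorded per trial. Protocol Section 9 requires only that assessments not done be reported as such, and no section shows that a per-trial reason is collected.

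Separately, reconcile the rest period in SAP 10.21 with the immediate second walk in Protocol 9.2.15.3, so that both describe the test that sites performed.

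The cost is a short text change and one derivation. The drawbacks are that the value rests on one walk for those patients, and that genuine inability to repeat the walk is not penalised.

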10.23 Adverse Events

Unless specified otherwise derivations will be applied to each adverse event (AE).

10.23.1 Start Date Imputation

Only start dates will be imputed.

Parameter	Missing	Additional Conditions	Imputation
Start date for AEs	D	M and Y same as M and Y of IMP Start Date	Date of IMP Start Date
		M and/or Y not same as date of IMP Start Date	First day of month but should fall on or after first IMP intake or if impossible after informed consent date
	D and M	Y same as Y of IMP Start Date	Date of IMP Start Date
		Y prior to Y of IMP Start Date but same as Y of informed consent date	Date of informed consent
		Y after Y of IMP Start Date	Use Jan 01 of Y
	D, M, Y	Not allowed by the system	Not applicable

AE = Adverse events; Jan = January; D = day; M = month; Y = year

Note: In all cases, if an estimated start date is after a complete stop date, use the first day of the stop date month.

10.23.2 COVID-19 Adverse event

A confirmed or suspected COVID-19 adverse event will be any adverse event for which the AE term or the preferred term include the text "COVID-19" but should not be "COVID-19 ELISA test negative".

For instance, confirmed COVID-19 Treatment emergent adverse event (TEAE) will be reported as:

- COVID-19 infection
- COVID-19 disease
- COVID-19 pneumonia
- COVID-19 respiratory infection
- Asymptomatic COVID-19

whereas a suspected COVID-19 AE will be coded as Suspected COVID-19.

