# 9.2.6 Concomitant Medication

Details of all current medications will be recorded. Any changes in concomitant medication during the trial must be recorded on the eCRF at trial visits. Patients should stop taking any prohibited therapy prior to Screening (Visit 1), as defined in Section 8.3.

Please note: Any vaccination related to COVID-19, that was received within the 12 months prior to Screening should be recorded as a concomitant medication. The information recorded should include the vaccine manufacturer and the dates of administration; differing start and end dates denoting two doses being received, if applicable.

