#### A) Adverse Event (Diagnosis or Syndrome if Known or Signs and Symptoms)

Where the investigator cannot determine a diagnosis, signs or symptoms should be recorded in the AE section of the eCRF. Once a diagnosis has been determined, the AE section of the eCRF must be updated to reflect the diagnosis in replacement of the original symptoms. In circumstances where only a provisional diagnosis is possible (working diagnosis), the eCRF must be updated to reflect the provisional diagnosis in replacement of the original symptoms. In some circumstances, it may be relevant for the investigator to include the symptoms alongside the diagnosis in the verbatim event description. However, the diagnosis (full or provisional) should be clearly stated, e.g., symptom due to disease (i.e., weakness due to cancer, tremor due to MS, headache and fever due to pneumonia, and generalized weakness due to hepatic cancer progression).

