12.8.1.2 Overall Adverse Event Summary

An overall adverse event summary will provide, by treatment arm, the number of adverse events as well as the number and percentage of patients with at least AE in the following categories:

- TEAE
- TEAE related to IMP
- Confirmed or suspected COVID-19 TEAE, (as described in Section 10.23.2)
- TEAE leading to permanent IMP discontinuation
- TEAE related to IMP leading to permanent IMP discontinuation
- Serious TEAE
- Serious TEAE related to IMP
- AE with outcome of death
- AE with outcome of death related to IMP.

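### The text search for COVID-19 adverse events in SAP 10.23.2 has one exclusion, so events that name COVID-19 without being an infection count as confirmed or suspected COVID-19

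*SAP*

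**What the plan says.** SAP 10.23.2 defines a confirmed or suspected COVID-19 event as "any adverse event for which the AE term or the preferred term include the text" 'COVID-19'. The verbatim term and the coded term are both searched, and a match in either is enough. One term, 'COVID-19 ELISA test negative', is excluded. Five infection terms follow, introduced by "For instance, confirmed COVID-19 Treatment emergent adverse event (TEAE) will be reported as", so they illustrate the rule and do not close it. A suspected case is said to be coded as Suspected COVID-19.

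The rule feeds the row "Confirmed or suspected COVID-19 TEAE, (as described in Section 10.23.2") of the overall summary in SAP 12.8.1.2. That row gives the number of events and the number and percentage of patients by treatment arm. The addendum (Table 7-1) keeps SAP 12.8.1 and does not list this row among the summaries it drops.

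Two protocol sections bear on vaccination. Protocol 9.2.6 states: "Any vaccination related to COVID-19, that was received within the 12 months prior to Screening should be recorded as a concomitant medication". Protocol 8.2 has any new treatment from Visit 1 onward recorded, which would include a vaccine dose given during the trial.

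**The concern.** A search for a word finds every event that mentions the disease, whether or not the patient had it. The SAP's exclusion of one negative test shows that its authors saw this, but it closes a single case. Terms for vaccination, immunisation, exposure and other negative tests remain inside the definition, and nothing else in the SAP or addendum removes them.

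What is at stake is the accuracy of one descriptive safety row. If such terms occur, a programmer who follows the SAP exactly will report too many COVID-19 cases. Correcting this by hand later would be an unplanned judgement, possibly made after unblinding.

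**Working it through.** The plan states no figure to reproduce. The check is to apply the rule as written, and then to trace which events can reach the row.

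**Step 1. The rule.** Count the event if 'COVID-19' appears in the AE term or the preferred term, unless the term is 'COVID-19 ELISA test negative'.

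**Step 2. Apply it to hypothetical AE terms.** None of these is trial data.

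| AE term | Counted? | An infection term? |
|---|---|---|
| COVID-19 pneumonia | yes | yes |
| Asymptomatic COVID-19 | yes | yes |
| Suspected COVID-19 | yes | suspected |
| COVID-19 ELISA test negative | no | no |
| COVID-19 PCR test negative | yes | no |
| Fever due to COVID-19 vaccination | yes | no |
| Sore arm after COVID-19 vaccine | yes | no |
| Reaction to COVID-19 booster | yes | no |
| Fever after vaccination | no | no |
| Sore arm after covid vaccine | no | no |

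Four of the ten terms are counted without describing an infection. For a vaccine reaction, coding the preferred term simply as fever or pain does not help, because a match on the AE term alone is enough. The last two rows show the limit: without the exact text, a vaccine reaction is not captured.

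**Step 3. Which events can reach the row.** SAP 12.8.1 counts an event as treatment-emergent if it first occurs on or after the IMP Start Date and before the IMP End Date + 30 days. Protocol 9.1.1 and 9.1.2 put Screening at least 28 days before Day 1. Reactions soon after the vaccinations covered by Protocol 9.2.6 therefore largely fall before treatment and outside the row. The relevant exposure is a vaccine given during the trial, recordable under Protocol 8.2.

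**Step 4. Where the rule is not used.** The efficacy analyses identify COVID-19 by other means:
- withdrawal reason, in the multiple imputation (SAP 12.5.2.2.1);
- protocol deviations, for the spasm count (SAP 12.5.2.3.4.3);
- investigator assessment, for the MSSS-88 (SAP 12.5.3.3.1.3).

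The addendum drops these sensitivity and supplemental analyses in any case.

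**Step 5. Size.** Let *c* be the proportion of patients with a true COVID-19 event, and *v* the proportion of other patients with a non-infection event that names COVID-19. The row shows *c* + *v*, so it is inflated by (*c* + *v*)/*c* = 1 + *v*/*c*. The documents give neither quantity. With *c* assumed to be 5%:

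| Assumed *v* | 1 + *v*/*c* |
|---|---|
| 0% | 1.0 |
| 0.5% | 1 + 0.5/5 = 1.1 |
| 1% | 1 + 1/5 = 1.2 |
| 5% | 1 + 5/5 = 2.0 |
| 10% | 1 + 10/5 = 3.0 |

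The answer is set entirely by the assumed *v*.

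**The case against.** The strongest reply is that nothing shows such terms will be recorded. Protocol 12.6 A says "it may be relevant for the investigator to include the symptoms alongside the diagnosis in the verbatim event description", but its pattern is a symptom due to a disease, with examples such as "headache and fever due to pneumonia". A vaccination is neither a disease nor a diagnosis. This stands: the protocol does not bar a verbatim that names a vaccine, but it does not invite one either.

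The consequence is also small and visible. The row is descriptive, with no test or decision attached. The listings in SAP 12.8.1.1 show the preferred term and the investigator's term, and SAP 12.8.1.3 tabulates all treatment-emergent events by preferred term. A reader could find a misclassified event. This also stands and limits the importance of the point. It does not make the row right.

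A reader might also infer that the rule misses positive tests coded to a preferred term without the text. That overlooks the match on either field. A verbatim of 'positive COVID-19 test' is caught whatever its preferred term, and Protocol 12.2 describes the reportable event in much those words. A positive test is missed only if both fields lack the text. For the same reason, a definition based on preferred terms alone would discard a useful check.

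**Conclusion.** The point holds as a minor correction. The rule, followed literally, misclassifies any treatment-emergent event that names COVID-19 in either field without being an infection, apart from the one excluded test. The effect can only raise the confirmed-or-suspected row of SAP 12.8.1.2, and its size is unknown.

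Two stronger readings are not supported. One is that vaccine reactions in general are counted as COVID-19: only those whose AE term or preferred term contains the exact text are. The other is that the row would be two or three times too high: that needs 5% to 10% of patients to have such an event against 5% with true COVID-19, and no document supports those rates. The conclusion rests on reading the five listed terms as examples, which is how the SAP introduces them.

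**What to change.** In SAP 10.23.2, or in the addendum, both of which are to be approved before unblinding:

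- Keep the search for 'COVID-19' in the AE term and the preferred term, but as a screen and not as the definition.
- Extend the exclusion from the single ELISA term to all vaccination- or immunisation-related, exposure-only and negative-test terms.
- Add positive-test terms that lack the text in both fields.
- Finalise the resulting list of events by blinded review before unblinding, and use that list for the row in SAP 12.8.1.2.

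The cost is a brief blinded review of terms and a few lines of text. No new data are needed and no other planned output changes.
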